8.3.2. QUALITY ASSURANCE

- 8.3.2.1.BENCHMARK (DRY RUN) CASE REVIEW: all potential sites shall receive, prior to patient enrollment, an anonymous electronic patient data set. A treatment plan shall be developed, and the plan reviewed by the PI and Physics Chair; completion of a satisfactory plan is required prior to patient enrollment.
- 8.3.2.2.FIRST PATIENT PRE-TREATMENT REVIEW: the treatment plan of the first patient enrolled at each site must be reviewed prior to beginning radiosurgery. The Principal Investigator (PI) shall be notified at the time of enrollment of this first patient, and of the proposed first treatment date, to assure PI's availability for review. After planning is complete, the treating site will review the treatment plan with the PI and Physics Chair, either remotely through a webcast or similar technique or via overnight delivery of documents to the PI site. The treatment planning data includes the fused primary and secondary imaging studies, contour sets and isodose distributions/DVHs, as well as the pre-treatment planning preparation form, CyberKnife treatment planning form and treatment plan QA form. If the treatment plan data are sent via overnight mail, the Principal Investigator and Physics Chair shall complete review within 3 working days of receipt; treatment will only begin after any necessary corrections are implemented and final plan is approved.
- 8.3.2.3.POST-TREATMENT REVIEW: The PI site will also review treatment plans and treatment delivery records for additional protocol patients:
- 8.3.2.4.The TREATMENT PLANS of up to the first THREE protocol patients for all participating radiation oncologists, urologists, and physicists may be reviewed, at the discretion of the Principal Investigator and Physics Chair. Also, treatment plans and treatment delivery records of THREE additional RANDOMLY chosen cases from each site will be reviewed. If warranted by the outcomes of above QA reviews, the PI may request that additional cases be submitted for review prior to further patient treatments.
 - 8.3.2.4.1. For patients chosen for post-treatment review, the study Monitor will notify the treating site no sooner than 1 day, but no later than 7 days, after completion of treatment. Within one week, the treating site will deliver to the PI site: 1) Deidentified copy of the treatment planning data sets (including fused primary and secondary imaging studies, contour sets, and isodose distributions/DVHs), 2) Copies of the Pre-treatment Planning Preparation form, CyberKnife Treatment Planning form, and Treatment Plan QA form, 3) CyberKnife Treatment form, and screen captures documenting treatment delivery for all fractions. These will be reviewed by the PI and Physics chair within one week, with feedback given to the submitting site as needed.

8.3.3. EVALUATED STRUCTURES:

- 8.3.3.1.CTV: The Clinical Treatment Volume (CTV)
 - 8.3.3.1.1. LOW-RISK PATIENTS: (CS T1b-T2a, PSA 10, Gleason score 6): The CTV is the pre-registered MRI defined prostate volume, unless MRI-based imaging is medically contraindicated or judged inaccurate by the investigator (see

П

section 8.3.3.1.2.), in which case the CT may be used to define the CTV. Additionally, at the discretion of the investigator, some or all of the adjacent seminal vesicle volume may be included in the CTV for any of the following reasons: prostate base involvement by any criteria, perineural invasion, or equivocal MRI evidence of seminal vesicle invasion in a patient with no other clinical or pathological evidence for seminal vesicle invasion. In the event that the planning MRI reveals evidence for direct extracapsular invasion (Stage T3a) or seminal vesicle invasion (Stage T3b) that the investigator believes to be a true positive result, the patient will be withdrawn from the protocol and treated by an alternate method off protocol.

- 8.3.3.1.2. INTERMEDIATE RISK PATIENTS: (PSA > 10, Gleason = 7, or CS T2b) In addition to the above, the CTV will also include not less than 1.0 cm of seminal vesicle tissue volume adjacent to the prostate volume. MRI visible fiducials, if available, are encouraged for optimal prostate volume co-registration. If MRI and CT planning is done, and image co-registration is accurate within 2 mm in the opinion of the investigator, the MRI will be used as the CTV reference imaging modality. If CT and MRI are both done for planning purposes, but in the opinion of the investigator the co-registration of these modalities is not accurate within 2 mm (The most common cause of this will likely be differing degrees of rectal contents between the studies), CT will be used as the CTV reference imaging modality. The investigator will also have the discretion to repeat the planning MRI or CT. The investigator will specify whether CT or MRI is the CTV defining modality. In the event that the planning MRI reveals evidence for direct extracapsular invasion (Stage T3a) or seminal vesicle invasion (Stage T3b) that the investigator believes to be a true positive result, the patient will be withdrawn from the protocol and treated by an alternate method off protocol.
- 8.3.3.2.PTV: The prescription dose shall be delivered to the Planning Tumor Volume (PTV).
 - 8.3.3.2.1. LOW RISK PATIENTS (PSA < 10 ng/ml, T2a, Gleason Score 6): The PTV is an enlargement of the CTV. The CTV should be expanded to include a 2 mm margin at the proximal, distal, anterior, lateral and posterior aspects of the CTV. Posteriorly, where the CTV abuts the rectum, there will be no margin.

 - 8.3.3.2.2. INTERMEDIATE RISK PATIENTS (PSA 10.1 20 ng/ml or Gleason Score 7 or T2b): The PTV should be expanded to include a 2mm margin at the proximal, distal, anterior, lateral and posterior aspects of the CTV. A posterior-lateral margin expansion of 5 mm will be added on the side of the positive biopsy and on the side of palpable tumor. In other words, an intermediate-risk patient will have a unilateral or bilateral CTV PTV posterior-lateral margin expansion of 5 mm. If the side of the positive biopsy is unknown, or if it conflicts with the clinical T-stage findings, the posterior-lateral margin expansion of 5 mm will be done bilaterally. Posteriorly, where the CTV abuts the rectum, there will be no margin.
 - 8.3.3.2.3. PERINEURAL INVASION: Regardless of prognostic subset, a posterior-lateral margin expansion of 5 mm will be added on the side of the positive biopsy. If the side of the positive biopsy is unknown, or if it conflicts with the clinical T-stage findings, the posterior-lateral margin expansion of 5 mm will be done bilaterally. Posteriorly, where the CTV abuts the rectum, there will be no margin.

- 8.3.3.3.NORMAL TISSUES: CONTOURING REQUIRED: The structures listed below will be contoured and evaluated with DVH analysis. Bowel peristalsis and bladder filling change the size and location of normal structures. If the CT and MRI show normal tissues in different locations immediately adjacent (i.e., within < 2cm) the prostate, the contoured structure shall be a larger composite of both image sets. Grid size should be sufficiently large to include the entire structure.
 - 8.3.3.3.1. RECTUM: defined as the visible outer rectal wall, extending from 1.5 cm superior to 1.5 cm inferior to PTV.
 - 8.3.3.3.2. RECTAL MUCOSA: Defined as a 3.0 mm contraction of the rectum volume.
 - 8.3.3.3.3. BLADDER, defined as a solid structure including the bladder wall and lumen.
 - 8.3.3.3.4. URETHRA: To be defined by Foley catheter on planning CT. Approval by the Urologist or Radiation Oncologist is required.
 - 8.3.3.3.5. PENILE BULB: Will be defined only if image co-registered MRI is used in the planning process. The penile bulb is defined as the portion of the bulbous spongiosum that lies inferior to the urogenital diaphragm.
 - 8.3.3.3.6. NEUROVASCULAR BUNDLE, if visible on MRI or CT: should be contoured in transverse planes extending from the prostatic apex to the base.
 - 8.3.3.3.7. SIGMOID COLON OR OTHER BOWEL lying within 2 cm of the PTV should be contoured.
 - 8.3.3.3.8. TESTES, bilateral shall be contoured.
- 8.3.4. DOSE SPECIFICATIONS: All specified doses are for the entire treatment course. All volume percentages are rounded to the nearest tenth of a percent for consistency, i.e. a volume of 0.02% shall be recorded as 0.0%.
 - 8.3.4.1.The PRESCRIPTION DOSE of 38 Gy delivered in 4 fractions of 9.5 Gy per fraction will be delivered in 7 days, with > 95% of the PTV encompassed within the prescription isodose volume.
 - 8.3.4.2.RECTUM OUTER WALL:
 - 8.3.4.2.1. Defined as the visible outer rectal wall, extending from 1.5cm. superior to 1.5cm inferior to PTV. Maximum dose (D_{max}): 100% of prescribed (38Gy)
 - 8.3.4.2.2. Minor variation: 100.1 110% of the prescribed dose (41.8 Gy).
 - 8.3.4.2.3. Major variation: > 41.8 Gy
 - 8.3.4.3.RECTAL MUCOSA:
 - 8.3.4.3.1. Defined as a 3.0 mm contraction of the Rectum outer wall volume. Maximum dose (D_{max}): 75% of prescribed (28.5Gy)
 - 8.3.4.3.2. Minor variation: Dmax > 75 90% of prescribed dose (34.2 Gy)
 - 8.3.4.3.3. Major variation: Dmax > 34.2 Gy
 - 8.3.4.4.BLADDER:
 - 8.3.4.4.1. Dmax: 120% of prescribed dose. Highest 10% (D₁₀): 110% of prescribed dose.
 - 8.3.4.5. **URETHRA**: To be defined by Foley catheter on planning CT
 - 8.3.4.5.1. Maximum dose: 120% of prescribed dose; Highest 10% (D₁₀): ≤110% of prescribed dose; Highest 50% (D₅₀): ≤ 105% of prescribed dose
 - 8.3.4.6.SIGMOID COLON AND OTHER BOWEL:

- Г
- 8.3.4.6.1. Sigmoid colon outer wall and other bowel outer wall within 2 cm of PTV: Dmax < 75% of prescribed (28.5Gy)
- 8.3.4.6.2. Minor variation: Dmax > 75 90% of prescribed dose (34.2 Gy)
- 8.3.4.6.3. Major variation: Dmax > 34.2 Gy
- 8.3.4.7.NEUROVASCULAR BUNDLE: Urologist or radiation oncologist contour approval required. D₉₀, D₅₀, D₁₀, D_{max}, V₁₀₀ and V₅₀ will be carried for possible dosimetry-morbidity correlation but no specific dosimetry constraint will be applied neurovascular bundle anatomy will be defined only if image co-registered MRI is used in the planning process. If it is the opinion of the urologist that the neurovascular bundle is not well visualized on MRI, this will be indicated on the reporting CRFs and the neurovascular bundle dosimetry parameters will not be reported for that patient.
- 8.3.4.8.PENILE BULB: Urologist or radiation oncologist contour approval required. D₉₀, D₅₀, D₁₀, D_{max}, V₁₀₀ and V₅₀ will be carried for possible dosimetry-morbidity correlation but no specific dosimetry constraint will be applied.
- 8.3.4.9.TESTES (bilateral) shall be contoured, and no primary beams shall traverse this structure. The D50 will be recorded.
- 8.3.4.10. **CONFORMALITY INDEX FOR NORMAL TISSUES**: The ratio of the prescription isodose volume to the PTV will be ≥1.0 and ≤1.5. Minor variation: ≤ 0.99 or ≥1.51 2.0
- 8.3.4.11. DOSE INHOMOGENEITY FOR NORMAL TISSUES: The PTV volume receiving at least 150% of prescription dose (57 Gy) will be > 1%, without a specific maximum limitation, provided other normal tissue dosimetry constraints are met. This translates to a prescription isodose line that does not exceed 66%. More typically, it is expected that the prescription isodose line will be in the range of 50-59% for patients in this protocol.
- 8.3.5. WORK EFFORT: for all involved disciplines (radiation oncologist, urologist and physicist), the time spent performing the various aspects of treatment planning will be recorded.

8.4. CYBERKNIFE TREATMENT DELIVERY

- 8.4.1. The prescribed PTV dose of 38Gy shall be given in 4 fractions using the CyberKnife.
- 8.4.2. Bowel/bladder preparation:
 - 8.4.2.1. The rectum will be emptied of its contents by use of one or more Fleets enemas prior to the planning CT and MRI scans.
 - 8.4.2.2. There will be no fluid intake by the patient within 4 hours prior to a planning study. If the patient takes a diuretic, that medication will not be taken that day until after the planning study(s) have been completed. The bladder will be drained completely through the use of a Foley catheter and then refilled with 100cc of sterile water prior to the planning CT and prior to the planning MRI scans. If CT and MRI scans are done consecutively, the bladder will be drained between these studies and refilled with 100 cc of sterile water immediately prior to the second study.
 - 8.4.2.3. The planning CT and MRI scans will be done with a Foley catheter in place to define the course of the urethra through the CTV. To improve comfort and minimize inconvenience to the patient, if possible, the CT and MRI planning studies will be done consecutively.

- 8.4.3. Treatment should be completed within 7 days.
- 8.4.4. At least three fiducials should be identified for each treatment. If fewer than three fiducials can be tracked, then additional fiducials will be placed, and the patient replanned. Every effort will be made to treat using rotational corrections. The treatment system will be set to record rotations on the treatment printout. On a given treatment, if rotational corrections are not possible, treatment may continue, with rotational deltas recorded, as long as these remain below 2 degrees. For subsequent treatments, diet changes or additional bowel preparations will be made, and/or rectal tube placed, and treatment shall be attempted using rotational corrections. If treatment proceeds without rotational corrections, the therapist shall inform the attending radiation oncologist, and record the duration of treatment performed without rotations.
- 8.4.5. On the day of the CyberKnife treatment, the patient will be taken into the CyberKnife system treatment room, set up in their respective immobilization devices and positioned on the CyberKnife couch. X-rays will be taken with the CyberKnife system to ensure that the tumor is aligned in a manner consistent with the position in which the treatment plan CT image was taken. Target movement is expected to require imaging every 1-3 nodes, per the discretion of the attending physician, and in no situation should imaging occur less frequently than every 5 nodes. Fiducial locations in the images will be extracted and compared to the fiducial locations in the CT scans to estimate target movements. The following planning and treatment information shall be recorded for every plan and fraction delivered: set-up time required, number of nodes treated, number of nodes treated with rotational corrections, number of nodes imaged, and total treatment time. This data will be collected onto Case Report Forms.
- 8.4.6. All planned nodes will be treated whenever possible. If treatment must be terminated prematurely on fractions 1-3, compensate as follows. If 2/3 or more of all non-zero nodes were treated, then the untreated nodes plus the full next fraction should be treated on the next treatment day (this should introduce an error of < 5% in BED delivered). If fewer than 2/3 of the non-zero nodes were treated, then the untreated portion of this fraction (only) will be made up for on the following day. The subsequent fraction shall be delivered on the next treatment day. If treatment must be terminated prematurely on the fourth fraction, and 90% of the non-zero nodes were treated, then no further treatment shall be given (this should introduce an error of < 5% for total BED delivered). If fewer than 90% of the non-zero nodes were treated, then the deficit shall be delivered on the following treatment day. All such variations shall be recorded.
- 8.4.7. WORK EFFORT: for all member of the treatment team (therapist, physicist, radiation oncologist, and urologist), time spent actively involved with treatment shall be recorded. Also required on-site supervisory time will be recorded.

9. PATIENT ASSESSMENTS AND TOXICITY

Assessment Preentry On tx day 4 Follow-up interval: months post therapy Years post therapy

History Physical exam (DRE) ECOG Performance Scale Prostate Biopsy & Gleason score ^a	x x x x		1 wk	1 X	3 X X X	6 X X X	12 X X X	18 X X X	24(every 6 mo up to 5 years) X ^b X ^b X ^b X	6-10
PSA	X				X	X	X	X	$\mathbf{x}^{\mathbf{b}}$	X
Prostate volume assessment Testosterone CBC, platelets BUN, creatinine	X X X X	.,	•	•	x	x	x	x	x	.,
Toxicity evaluation	X	X	X	X	X	X	X	X	$\mathbf{x}_{\mathbf{p}}$	X
AUA score	X	X	X	X	X	X	X	X	X*	X
SF-12	X			X		X	X		X*	
EPIC-26 Questionnaire	X			X		X	X		X*	X
SHIM Questionnaire	X			X		X	X		X*	X
Utilization of Sexual Rx/Devices	X			X		X	X		X*	

- a. Central review of pathology; biopsy recommended at 2 yrs, & required at time of failure
- b. Continue every 6 months through year 5
- * . Continue every 12 months through year 5.

9.1. EVALUATION DURING TREATMENT & FOLLOWING TREATMENT

- 9.1.1. PRE-ENTRY ASSESSMENT: see section 4.7.
- 9.1.2. Stereotactic radiosurgery is an outpatient procedure. Patient management immediately after the procedure will follow routine patient care guidelines as determined by the physician. Subjects will be provided instructions on who to call with specific contact information, in the event they experience any untoward effects following treatment. In the event a subject experiences any untoward effects following CyberKnife treatment, information specific to the patient's condition and symptoms, treatment intervention required, and hospital stay and course will be recorded for purposes of clinical evaluation.
- 9.1.3. ACUTE ASSESSMENT: Patients will have toxicity evaluation and AUA score on the last day of treatment.
- 9.1.4. ASSESSMENTS FOLLOWING TREATMENT: at one week after treatment (allowed window: +/- 3 days), toxicity and AUA score will be evaluated. At 1 month (+/- 7 days) following treatment, patients will be assessed for acute toxicity, and will fill out AUA form, SF-12, EPIC-26, SHIM and Utilization of Sexual Rx/Devices. At 3, 6, 12, 18, and 24 month (+/- 2 wks) intervals (and every 6 months thereafter, through year 5), patients will be seen and evaluated, including a history, physical exam, ECOG performance status, PSA, toxicity evaluation, and AUA score. In addition, at 6 months, 12 months and annually thereafter, the SF-12, EPIC-26, SHIM and Utilization of Sexual Medications/Devices will be administered. After the 5 year follow-up patients will be seen yearly through year 10 (allowed window: +/-1 month) and the following will be performed: PSA, toxicity evaluation, and the following questionnaires will be administered: EPIC -26; AUA; SHIM. Examination and studies may

- be done at outside facility. A serum total testosterone will be measured at baseline and with every PSA through year 2.
- 9.1.5. PROSTATE BIOPSY will be performed at time of biochemical or local clinical failure, and is encouraged at 2 years following treatment and at time of distant failure.
- 9.1.6. BONE SCAN will be performed at the time of biochemical failure, or when the patient develops signs of symptoms suggesting metastatic disease.
- 9.1.7. Axial Imaging (CT or MRI) of the abdomen and pelvis will be performed at the time of biochemical failure, or when the patient develops signs of symptoms suggesting metastatic disease.

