11.4.2. SECONDARY OBJECTIVES

1. Local and Distant Tumor Control

As defined in Section 9.4, the failure to achieve local and distant tumor control will be documented for each patient. These rates will be summarized and descriptive statistics (standard deviations, confidence intervals) will calculated.

2. Quality of Life Assessments

The SF-12 total score, AUA score, EPIC-26 total score and the EPIC-sexual domain sub score are used to quantify quality of life (QoL) at baseline and repeatedly during the post treatment period (see Section 9.0). We will use the generalized estimating equation (GEE) method to provide valid inferences. This method was originated to make inference about average behavior, where the dependent variable depends not only on the "explanatory" variable (time measured in months) but also on the correlation of a patient's repeated measurements. The GEE approach fits the model to the observed data as closely as possible, weighting each patients' "cluster" of measurements over time inversely to its variance - covariance matrix. With this method, no imputations are required and all data recorded is use in the analysis. Other important features of GEE are that no distributional assumptions for the dependent variable are required to use the method and in most cases valid inferences are provided even when the correlation structure is miss-specified. For each score, we will use GEE to fit a straight line to patients' longitudinal course of repeated values. We hypothesize that immediately following treatment, the GU & GI subsections of the EPIC-26 and the AUA will demonstrate a worsening of GU and GI function, but this will return to normal with time. We further hypothesize that the sexual function subset of the EPIC-26 will show gradual worsening function relative to baseline over the five-year follow-up period. These QOL outcomes will be compared to those reported in other prospective studies using the same instruments, including RTOG 0232

and 0415. We hypothesize that the slope of a fitted line will not be significantly less than zero; that is, QoL will be maintained throughout the assessment period.

3. Adverse Events

All adverse events will be recorded on the case report forms. For both acute (<=90 days of treatment start) and late (>90 days of treatment start), the frequency and proportion of each type of adverse event will be presented in tabular form, on both a per-patient and a per-event basis.

4. Survival

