Appendix VI: AUA, SF-12, EPIC, SHIM, USMD Questionnaires:

American Urological Association (AUA) symptom index: was developed to help men determine how bothersome their urinary symptoms are and to check the effectiveness of treatment.⁶ This questionnaire has also been adopted worldwide and is known as the International Prostate Symptom Score (IPSS). It is sometimes seen with a Quality of Life Scale at the end of the questionnaire.

Name:	Today's date:

(Circle one number on each line)	Almost never	Less than 1 time in 5	Less than half the time	About half the time	More than half the time	Almost always
Over the past month or so, how often have you had a sensation of not emptying your bladder completely after you finished urinating?	0	1	2	3	4	5
Over the past month or so, how often have you had to urinate again less than two hours after you finished urinating?	0	1	2	3	4	5
Over the past month or so, how often have you found you stopped and started again several times when you urinated?	0	1	2	3	4	5
Over the past month or so, how often have you found it difficult to postpone urination?	0	1	2	3	4	5
Over the past month or so, how often have you had a weak urinary stream?	0	1	2	3	4	5
Over the past month or so, how often have you had to push or strain to begin urination?	0	1	2	3	4	5
	None	1 time	2 times	3 times	4 times	5 or more times
Over the past month, how many times did you most typically get up to urinate from the time you went to bed at night until the time you got up in the morning?	0	1	2	3	4	5

 Quality of Life: If you were to spend the rest of your life with your urinary condition just the way it is now, how would you feel about that? Delighted, Pleased, Mostly satisfied, Mixed, Mostly dissatisfied, Unhappy, Terrible

SF-12 (Short Form)

 In general, would you say your health is excellent, very good, good, fair, or poor? Excellent ... Very Good ... Good ... Fair ... Poor ...

The following items are about activities you might do during a typical day. Does your health now limit you in these activities? If so, how much?

- 2) First, moderate activities such as moving a table, pushing a vacuum cleaner, bowling or playing golf. Does your health now limit you a lot, limit you a little, or not limit you at all. Limited a lot ... Limited a little ... Not limited at all ...
- 3. Climbing several flights of stairs. Does your health now limit you a lot, limit you a little, or not limit you at all? Limited a lot ... Limited a little ... Not limited at all ...

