9. How would you describe the usual QU	JALITY of	your erections	s during th	e last 4 week	s?	
None at all				1		
Not firm enough for any sexual a	ctivity		****	2		
Firm enough for masturbation an	d foreplay	only		3 (Circle	e one number)	59
Firm enough for intercourse				4		
10. How would you describe the FREQU	ENCY of y	our erections	during the	e last 4 week	s?	
I NEVER had an erection when I						
I had an erection LESS THAN HA	ALF the tin	ne I wanted or	ne	2		
I had an erection ABOUT HALF t	he time I v	vanted one		3 (Circle	e one number)	60
I had an erection MORE THAN H	ALF the ti	me I wanted o	ne	4		
I had an erection WHENEVER I	wanted on	e		5		

						Do Not Mark in This Space
11. Overall, how would you rate your ability	to funct	ion sexually	during the la	ast 4 weeks?		
Very poor		1				
Poor		2				
Fair		3	(Circ	le one numbe	r)	64/
Good	Good					
Very good		5				
during the last 4 weeks? No problem	**********	2 3 4 5		de one numbe	i.	68/
(Circle one number on each line)	No roblem	Very Small Problem	Small Problem	Moderate Problem	Big Problem	
a. Hot flashes	0	1	2	3	4	74/
b. Breast tenderness/enlargement	0	1	2	3	4	75/
- FE dd	0	1	2	3	4	77/
 Feeling depressed 						
d. Lack of energy	0	1	2	3	4	78/

THANK YOU VERY MUCH!!

EPIC-SF 6.2002

Copyright 2002. The University of Michigan. All rights reserved.

Г

SEXUAL HEALTH INVENTORY FOR MEN (SHIM)

PATIENT NAME:	TODAY'S DATE:
---------------	---------------

PATIENT INSTRUCTIONS

Sexual health is an important part of an individual's overall physical and emotional well-being. Erectile dysfunction, also known as impotence, is one type of very common medical condition affecting sexual health. Fortunately, there are many different treatment options for erectile dysfunction. This questionnaire is designed to help you and your doctor identify if you may be experiencing erectile dysfunction. If you are, you may choose to discuss treatment options with your doctor.

Each question has several possible responses. Circle the number of the response that **best describes** your own situation. Please be sure that you select one and only one response for **each question**.

OVER THE PAST 6 MONTHS:

How do you rate your confidence		Very Low	Low	MODERATE	Нідн	VERY HIGH
that you could get and keep an erection?		1	2	3	4	5

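### The AUA's one-month recall does not fit its last-treatment-day and 1-week administrations, and SHIM's six-month recall does not fit its 1-month administration, so these scores largely describe the time before treatment

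*Combined protocol and SAP*

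**What the plan says.** Section 9.1.3 sets the first on-study AUA: "Patients will have toxicity evaluation and AUA score on the last day of treatment". Section 9.1.4 sets the next: "at one week after treatment (allowed window: +/- 3 days), toxicity and AUA score will be evaluated". It then adds the first SHIM after treatment: "At 1 month (+/- 7 days) following treatment, patients will be assessed for acute toxicity, and will fill out AUA form, SF-12, EPIC-26, SHIM". On course length, section 8.4.3 says: "Treatment should be completed within 7 days".

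Appendix VI prints the forms. A typical AUA item reads "Over the past month or so, how often have you had a weak urinary stream", and the nocturia item begins "Over the past month, how many times did you most typically get up to urinate". SHIM is headed "OVER THE PAST 6 MONTHS". The EPIC-26 items ask about the last four weeks.

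Section 11.4.2 names the SF-12 total, the AUA, the EPIC-26 total and the EPIC sexual sub-score as the quality-of-life measures. It fits a straight line to each by GEE and says that all recorded data are used. SHIM is not on that list. The section also states: "We hypothesize that immediately following treatment, the GU & GI subsections of the EPIC-26 and the AUA will demonstrate a worsening", followed by a return to normal.

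The documents give no shortened-recall form, no instruction to answer only for the time since treatment, and no rule to set these visits apart.

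**The concern.** A questionnaire describes the period it asks about, not the day it is filled in. Where most of that period lies before the first fraction, the score is a mixture of pre-treatment and post-treatment function, although the schedule labels it as an assessment during or after treatment.

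For the AUA this reaches a planned analysis. The last-day and one-week scores are two of the four AUA points from the end of treatment to month 3 (last day, 1 week, 1 month, 3 months), and 11.4.2 uses them like any other. A small rise at these visits could be reported as a mild acute urinary effect when part of it comes from the recall period.

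For SHIM the risk lies in reporting. Section 1.14 names better preservation of potency as a potential benefit, and section 1.15 plans to compare questionnaire results on sexual function with published results. A 1-month SHIM near baseline could be taken as early preservation when it mostly reports function before treatment.

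**Working it through.** The plan states no figure on this point, so there is none to reproduce.

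**Inputs**
- Course length c: 4 to 7 days. The upper end is from section 8.4.3. The lower end assumes four fractions on four consecutive days.
- Days since the last fraction d: 0 (last day); 7, range 4-10 (one week); 30, range 23-37 (one month). From 9.1.3 and 9.1.4.
- Recall R: AUA 30 days, with 28-42 tried because the wording is loose; SHIM 182.6 days; EPIC-26 28 days. From Appendix VI.

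**Formula.** Share of the recall window before the first fraction = max(0, 1 − (c + d)/R).

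**The three visits in question**
- AUA, last day: 1 − 4/30 = 87%; 1 − 7/30 = 77%.
- AUA, one week: 1 − 11/30 = 63%; 1 − 14/30 = 53%. Across the ±3-day window: 1 − 8/30 = 73% to 1 − 17/30 = 43%.
- SHIM, one month: 1 − 34/182.6 = 81%; 1 − 37/182.6 = 80%. Across the ±7-day window: 1 − 27/182.6 = 85% to 1 − 44/182.6 = 76%.

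**Visits where recall fits**
- AUA, one month: 0% at the nominal day; at most 1 − 27/30 = 10%.
- EPIC-26, one month: 0%; at most 1 − 27/28 = 4%.
- SHIM, six months (±2 weeks): 0%; at most 1 − 172.6/182.6 = 5%.

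**Sensitivity to the AUA recall length.** With 28 days the shares are 75-86% (last day) and 50-61% (one week, nominal). With 42 days they are 83-90% and 67-74%, and the month-1 AUA then has 12-19% before treatment at the nominal day.

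**Illustration of dilution.** The assumptions are that men average evenly over the window, that the change is complete at the first fraction, and that symptoms before treatment equal baseline. The observed change is then the true change × (c + d)/R. A 5-point AUA rise, chosen only for illustration, would read as:
- last day: 5 × 4/30 = 0.7 to 5 × 7/30 = 1.2 points;
- one week: 5 × 11/30 = 1.8 to 5 × 14/30 = 2.3 points.

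At the other extreme, if men answer only for how they feel that day, all 5 points appear. The documents do not say where between these ends the truth lies.

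**The case against.** The strongest reply is that little depends on these scores, and much of it stands.

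- **SHIM.** It is not among the measures analysed in 11.4.2. The only sexual-function hypothesis there concerns EPIC-26 and predicts gradual worsening. A reader might infer that the 1-month SHIM biases a planned test, but the documents contain no such test.
- **The acute-worsening hypothesis.** A reader might infer that it rests on the last-day and one-week AUA. It does not: it covers the EPIC-26 urinary and bowel subsections and the AUA together. EPIC-26 is first given after treatment at month 1, when the AUA is given too and its recall fits, so the hypothesis can be tested on matched data.
- **Direction.** The weeks before the first fraction are not simply baseline. Fiducials are placed at least 7 days before planning imaging (8.2.1), and planning uses a Foley catheter (8.2.4). The last-day AUA window reaches back 23 to 26 days before the first fraction (30 − 7 and 30 − 4), so symptoms from these procedures may fall inside it and raise the score. That early harm is understated is therefore not established.
- **The model.** A straight line fits a worsen-then-recover course poorly even with perfect early scores. Since a higher AUA is worse, low early values tilt the line towards worsening over time; they do not hide lasting harm.
- **Safeguards.** Toxicity is graded at the same early visits, and no decision rule uses AUA or SHIM.

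What remains is the mismatch itself. The early AUA scores enter the model unmarked, and nothing warns a reader of the 1-month SHIM what period it covers. Toxicity grading does not fully replace the AUA there, since section 1.12 regards patient report as more sensitive than physician report.

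**Conclusion.** The mismatch is in the documents and is confined to three administrations. At nominal timing with a 30-day AUA recall, the pre-treatment period fills most of the window at each. It is a large majority for the last-day AUA and the 1-month SHIM. It is only a modest majority for the one-week AUA, where it can fall below half late in the visit window.

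These scores may understate early change if men average over the window. The documents cannot show that they do, or by how much.

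The analytic consequence is limited to the AUA model in 11.4.2. For SHIM it is limited to descriptive reporting and comparison with the literature. A reader might extend the point to the safety conclusion, but the primary safety endpoint and the stopping rule count toxicity of grade 3 or higher, and the primary efficacy endpoint is biochemical. Neither uses these questionnaires. This is a worthwhile correction to a secondary analysis.

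**What to change.** Amend section 11.4.2 as follows.

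- Keep collecting the last-day and one-week AUA. Report them descriptively, labelled as overlapping the pre-treatment period.
- Alongside the GEE as written, fit the AUA model with month 1 as the first post-treatment value. Rest any statement about acute urinary change on month 1.
- Treat month 6 as the first post-treatment SHIM. For sexual function at month 1, use the EPIC-26 sexual domain, whose recall fits that visit.

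The cost is a few sentences and one extra model fit; no new data are needed. Section 11.2 reports an interim analysis at 4,512 months of follow-up against a basis of 260 subjects, about 17 months each (4,512/260), so many early visits have probably passed and analysis wording is the practical remedy.

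The downside is that, before month 1, the acute urinary effect would rest mainly on clinician toxicity grading, with the early AUA as descriptive support. That is why those scores should be kept and labelled rather than discarded.
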